## **List of Abbreviations:**

VAS=Visual Analog Scale  
FNB=Femoral Nerve Block  
SNB=Sciatic Nerve Block

## **1. Research Synopsis**

Purpose of this study is to investigate the pain outcomes and satisfaction of pain relief for pediatric patients receiving needless jet-injected (J-Tip) lidocaine prior to regional anesthesia with femoral and/or sciatic nerve block and general anesthesia for arthroscopic knee surgery compared to femoral nerve block and/or sciatic nerve block with needle injected lidocaine prior to regional and general anesthesia.

### **1.1 Study Title**

Randomized Prospective Trial of Needleless Jet Injected (J-Tip) Lidocaine in Children Undergoing Regional Block Anesthesia prior to knee arthroscopy.

### **1.2 Study Population**

Children of both sexes, between the ages of 11 and 17 undergoing arthroscopic knee surgery will be eligible for this study.

### **1.3 Study Design**

This study is a prospective and randomized project.

### **1.4 Sample Size**

A sample size of 50 per group, two groups, for a total of 100 patients is the goal. An additional 15 patients will be enrolled to account for withdrawals, bringing total enrolled to 115.

### **1.5 Study Duration**

This study is estimated to take 3 years to complete, including the length of time to review charts, data collection, and analysis of study data.

### **1.6 Primary Objective**

The primary objective is to measure the change in pain from a femoral or sciatic nerve block with the use of J-tip injected lidocaine compared to needle injected lidocaine for local anesthesia prior to the regional nerve block.

### **1.7 Secondary Objectives**

- To evaluate the difference in pain from local anesthetic infiltration with J-tip needless injection compared to needle injection.
- To evaluate efficacy of femoral and/or sciatic nerve block after J-tip lidocaine injection compared to needle injected lidocaine post operatively by tracking pain levels to post operative day three.
- To assess patient and parent satisfaction with J-tip use.
- To assess changes in post operative pain medication amounts with J-tip use.
- To evaluate changes in post operative nausea and/or vomiting with J-tip use.
- To evaluate changes in post operative anti-nausea/anti-emetic medication use with J-tip use.
- To evaluate changes in time of PACU stay.

- To assess any differences in outcomes or pain after J-tip or needle injected lidocaine with respect to BMI, thigh circumference, gender, ethnicity or operative time in pain reporting measures, satisfaction or medication usage.

## **2. Background and Significance:**

Lower extremity regional nerve block anesthesia has been shown to decrease post-operative pain and length of hospital stay after arthroscopic knee surgery (Nowicki, Micalizzi, Schloss). The introduction of the nerve block needle is still a source of pain and anxiety for the pediatric patient. The pain experienced during the nerve block procedure may cause difficulty in technique allowing for the most efficient nerve blockade. Infiltration of the subcutaneous tissues with local anesthetic is usually performed prior to nerve block needle introduction. This is performed by standard techniques with needle and syringe and is associated with the pain usually experienced with one or more needle sticks required to fully deposit the local anesthetic. It has also been suggested that post block complications are higher in pediatric patients receiving nerve blocks while awake or sedated compared to patients already under general anesthesia (Taenzer). For this and other reasons, many of these blocks are performed with the patient already in the operating room under a general anesthetic. This can increase operating room time and expense for each surgical case

Patients have benefited from the increasing use of lower extremity regional block anesthesia for arthroscopic knee surgeries. This benefit has been realized by patients with regard to decreased pain post operatively. The health care system and patients share the benefit of decreased length of hospital stay and significantly fewer patients admitted to inpatient status. Current practices with anesthesia for pediatric patients undergoing knee surgery is variable. General anesthesia is the norm during arthroscopic knee surgery, but the introduction and timing of regional blocks is physician and institution dependent. In some cases femoral and sciatic blocks are used and in others only femoral blocks are used. Some are introduced prior to leaving the preoperative area, after general anesthesia has been administered, while still under general anesthesia after the procedure is complete, or in the post anesthesia care unit with the general anesthetic effects diminishing. Most blocks at Arnold Palmer medical center are administered in the preoperative area prior to patient transfer to the operating room.

The J-tip has not been reported for use prior to regional block anesthesia prior to femoral or sciatic nerve blocks. The use of the J-tip for lidocaine introduction prior to femoral or sciatic blocks at Arnold Palmer Medical Center has been up to the discretion of the anesthesiologist. It has been anecdotally reported at our institution to have equal or better pain relief for the regional nerve blocks as needle introduction of lidocaine.

While there has been much attention appropriately directed to post operative pain control after arthroscopic surgery, minimal concern has been shown to decrease pain from regional block needle introduction. Needle insertion is the most common pain provoking procedure in the hospital setting. The American Academy of Pediatrics has addressed acute pain states with a policy statement expressing the need to anticipate, assess and manage pain caused by medical procedures. (AAP) There have been many advancements

to minimize the pain due to needle introduction for procedures such as venipuncture, intravenous cannulation and lumbar puncture (Ferayorni). It has been shown that anesthetic introduction by eutetic mixture of local anesthetics (EMLA) cream or needleless jet injection of local anesthetic reduces reported and observed pain and anxiety score validated measures when used prior to these procedures. There has been a demonstrated advantage in time to anesthesia and pain relief with needleless jet injection of lidocaine compared to EMLA cream use prior to venipuncture (Jimenez, Spanos, Zsigmond IJCPT 99). A decrease in pain has also been shown with jet-injected lidocaine over jet-injected placebo prior to needle insertions (Auerbach, Peter, Zsigmond JCA 99).

Limiting the use of pain medications and thus their potential side effects is becoming a greater point of emphasis in medicine. The use of opiate based medication to control acute pain from orthopaedic surgery is common. Utilization of these medications comes with possible pitfalls ranging from physiologic side effects to addiction. The most common side effects are manifested as nausea and vomiting. Control of these side effects often requires the administration of another pharmacologic agent. Within the field of orthopaedics, the use of regional block anesthesia prior to arthroscopic knee surgery has shown to decrease post-operative pain. This has lead to decreased opioid requirements. In turn this could provide for fewer medication-related side effects (Schloss). Local anesthesia prior to regional blockade may allow for a more effective block and permit the use of fewer pain medications and occurrence of side effects for those medications.

### **3. Objectives:**

#### **3.1 Primary Objective**

The primary objective is to measure the change in pain from femoral and/or sciatic nerve block with the use of the J-tip injector by visual analogue scales (VAS) for pain reporting.

#### **3.2 Secondary Objectives**

- To evaluate the difference in pain from local anesthetic infiltration with J-tip needleless injection compared to needle injection by use of VAS.
- To evaluate efficacy of femoral nerve block after J-tip lidocaine injection post operatively by use of VAS.
- To assess patient and parent satisfaction with J-tip use by satisfaction questionnaire.
- To assess changes in post operative pain medication amounts with J-tip use.
  - 1) Type and amount in PACU
  - 2) Home log of amount taken daily for post operative days one through three (Standard opiate based pain medication prescription given to each patient). Measured in number of pills/tablets taken each day.
- To evaluate changes in post operative nausea and/or vomiting with J-tip use.
  - Calculated as “Present” or “Absent”
- To evaluate changes in post operative anti-nausea/anti-emetic medication use with J-tip use.
  - 1) Type and amount in PACU

- 2) Home record log of amount taken daily (Standard medication prescription given to each patient). Measured in number of pills/tablets taken each day.
- To evaluate time in PACU with use of J-tip compared to needle use group prior to regional block. PACU stay time recorded in minutes.

#### **4. Study design/methodology:**

This study will be submitted to the Institutional Review Board of Orlando Health in Orlando, Florida, and will be conducted at Arnold Palmer Hospital from June 2015 to September 2017. Patients' age 11-17 years old undergoing knee arthroscopies are eligible for the trial. A single surgeon will perform all arthroscopic knee surgeries in this study. A femoral and/or sciatic block will be performed prior to the knee arthroscopic surgery. A single anesthesiologist will perform all J-tip or needle local anesthesia injections and nerve blocks in this study. Written consent is to be obtained from the parents or legal guardians, and written assent is to be obtained from the patients. The J-tip injector by National Medical Products, INC. will be used for needleless injection of 0.25 mL of 1% plain lidocaine or 1.5 mL of 1% plain lidocaine will be injected by syringe and 25-gauge needle into the subcutaneous tissues of the proximal anterior thigh near the inguinal crease prior to the femoral nerve block and the proximal posterolateral thigh near the gluteal fold or the posterolateral thigh prior to the sciatic regional nerve block. The location for the sciatic regional block along the course of the nerve will be chosen at the discretion of the performing anesthesiologist as is customary for sciatic nerve block procedures.

Patients with a known allergy to lidocaine, preoperative analgesic treatment with medications other than nonsteroidal anti-inflammatory drugs and acetaminophen, current use of chemotherapeutic agents, coagulation disturbance affecting coagulation abilities, any signs of skin infection or pathology at the injection site, neurosensory deficit at area of injection, developmental delay diagnosis precluding pain scale completion, and patients who received any other local anesthesia in the area of the regional block needle introduction prior to the regional block procedures will meet the exclusion criteria for this trial.

The J-tip will not be used for any IV insertions on patients in this study. There is currently variable use of the J-tip prior to IV insertions currently at Arnold Palmer Medical Center.

Demographics and anthropometric measurements considered in this study will be age, gender, ethnicity, thigh circumference and body mass index (BMI). Thigh circumference on the surgical side will be measured as 1/3 the distance distal to the ASIS to the superior pole of the ipsilateral patella.

Randomization to form the two trial groups will be performed by utilizing the computer program 'Research Randomizer' to create the randomization list. Randomization will be 50/50 or 1 to 1. The assignments will be printed out and placed into numbered envelopes.

The envelopes will be kept in a box in the [name] office. Group 1 will receive 0.25 mL of 1% buffered lidocaine delivered by the J-tip injector. Group 2 will be formed by subjects receiving 1.5 mL of 1% plain lidocaine injected by syringe and 25 gauge needle. The site of administration for this trial will be standard femoral and/or sciatic nerve block locations. The regional block will be performed under ultrasound guidance and with the assistance of nerve stimulation. General anesthesia will be given when the patient is in the operating room. This is done after the regional blocks have already been completed.

Administration of sedative and anxiolytic medications before or during the regional nerve block procedures will be based on nervous and pain VAS scores and anesthesiologist graded anxiety scores. If anxiety levels are indicated to be less than four, no sedation will be administered prior to the nerve block procedure. If anxiety scores are four to seven, then two mg to a maximum of four mg of Versed IV will be administered just prior to the local anesthesia administration. If anxiety scores are greater than seven, then two mg to a maximum of four mg of IV Versed will be administered just prior to the local anesthesia administration. If anesthesiologist observed anxiety levels remain above 7, then 20 mcg to a max of 40 mcg of IV Precedex will subsequently be administered.

The current observations of clinical efficacy in the delivery of local anesthesia by either needle or J-tip introduction have shown that the superficial and subcutaneous tissues are adequately anesthetized. Pain is usually encountered as the touhy needle, nerve block needle, penetrates the fascia of the muscle. The fascia is a barrier to the deeper tissues and is not anesthetized with any local anesthetic. Additional medications may be administered during the needle insertion through the fascia during the regional block. If pain VAS is greater than four, and IV Versed was not administered due to anxiety scores between four and seven, then two mg to a maximum of four mg of IV Versed will be administered. If pain continues to be above four and IV Precedex was not administered due to anxiety levels greater than seven, then 20 mcg to a max of 40 mcg IV Precedex will be administered. If pain continues to be greater than four, then 25 mcg Fentanyl to a maximum of 50 mcg will be administered. If pain values continue to be above seven, then 100 mg of IV propofol will be given. No matter what amount and type of sedative or anxiolytic is administered during the nerve block procedure, the first VAS measure at each time point will be the one of record for analysis in this study.

Patients will indicate their level of nervousness by completing a visual analogue scale, after admission to the preoperative area, for how nervous they are prior to their procedure. The anesthesiologist through observational measurement on a scale of 0-10 will also measure patient anxiety levels. A level of ten will be the highest observed measure of anxiety. These scores will assist in identifying patients that may need more general types of anesthesia prior to the nerve block. This will also allow for further evaluation of limitations due to the amount of pre-op anesthesia of patients in the study.

Femoral nerve blocks will be performed on all arthroscopic procedures. Single injection sciatic nerve blocks will be utilized in addition to femoral catheter nerve blocks for patients undergoing arthroscopic surgery with ACL reconstruction or if lateral meniscus repair is expected to be performed. The site or sites of injection on the operative lower extremity will be chosen, a timeout taken and sterile preparation performed by the

anesthesiologist prior to local anesthetic infiltration and the regional blockage needle introduction. After sterile preparation, the J-tip injector will be placed on the skin at the selected site of the regional block needle introduction. Firm pressure will be placed with the J-tip injector on the site for the chosen block, the safety ring slid down, the trigger pressed and the tip held firmly on the skin for three seconds. One quarter of a milliliter of one percent lidocaine will be injected with the characteristic “pop” and “hissing” sounds inherent to the J-tip injector. There is the possibility of medication leak and spray from under the J-tip. This is known to happen with use of the device and can be minimized with firm pressure of the device on the skin. Ninety seconds after the J-tip discharge, the regional block will be administered. The same initial timeout and sterile prep procedure will be followed for the use of local syringe and 25 gauge needle injection of 1% lidocaine ninety seconds prior to introduction of the regional block needle. The parents will be out of the room to reduce any effect on pain levels they could have by contact with the patient. Having the parents outside of the room is currently the standard during nerve block procedures at Arnold Palmer Hospital. No music, television, or video screen will be allowed to be on in the room from the time of the timeout to the completion of the post nerve block VAS completion to minimize confounders that could alter pain perception. Currently, there is no specific attention paid to whether or not music, television, or video screen is on during the procedure. There is varied and inconsistent use at this time.. If the sciatic regional block needle introduction is felt by the anesthesiologist to be an inadequate location, the procedure of local anesthesia and VAS questionnaires will be restarted and completed again for a new location. The new location will be at least two centimeters from the previous location. This will take into effect the local tissue dispersion of lidocaine shown to be about 1.8cm in diameter in previous needless injector studies (Hardison, Bennett). National Medical Products, INC. describes the dispersion of the medication delivered by the J-tip to usually be the size of the front diameter of the J-tip device, which measures one centimeter. The number of attempts with needle sticks for the regional block needle will be recorded for further analysis.

Times will be recorded for; time of J-tip administration, time of regional block performance, operating room arrival time, incision time, surgical end time, PACU arrival time and PACU discharge time. The amount of time from regional block to arrival in operating room and to incision time will be calculated. The surgical procedure time and amount of time in PACU will also be calculated.

Visual analogue pain scales will be completed prior to and immediately after J-tip use or needle local anesthesia infiltration. The scale immediately after will be with regard to pain felt at time of J-tip use or needle introduction. The scale will be completed once again prior to and immediately after needle introduction for each regional blockade. The scale immediately after will be with regard to pain felt at time of regional block needle introduction. Visual analogue pain scale will be recorded in PACU. All scoring will be performed on separate VAS assessments without patient access to previous scores.

The patient will record visual analogue pain scales on post-operative days one through three. The anesthesiologist will collect telephone verbal pain scores on a 0-10 scale on post-operative days one and two. This is current standard procedure for all patients who

receive a regional block. The femoral nerve block catheter, when utilized, is left in place for 40 hours from the initial femoral nerve block procedure. The number of days until the post-operative visit will be recorded. Another visual analogue pain scale will be completed at the first post-operative visit. An Arthroscopic Surgery Satisfaction Questionnaire will be completed by the patient and a parent or guardian at the first post-operative visit. The questionnaire will be specific to the patient's randomized treatment group. If the patient was randomized to receive the J-Tip, the patient and parent will receive the J-Tip questionnaire and if the patient was randomized to receive the traditional needle and syringe, the patient and parent will receive the needled syringe questionnaire. The sex of the parent or guardian completing the form will be recorded.

It will also be recorded if intra-articular analgesic injection is given intra-operatively. The amount and type of pain and anti-nausea/emeitic and pain medication use will be recorded in PACU and by the patient on the first three post-operative days.

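### Section 4 defines the J-Tip arm's lidocaine as both plain and buffered, and under neither version can the infiltration-pain difference be credited to the device alone

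*Combined protocol and SAP*

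**What the plan says.** Section 4 (Study design/methodology) describes the local anesthetic in three places.

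- **Opening paragraph.** The J-Tip injector "will be used for needleless injection of 0.25 mL of 1% plain lidocaine or 1.5 mL of 1% plain lidocaine", the second volume being for the syringe and needle. Both arms are plain.
- **Group definitions, in the randomization text.** "Group 1 will receive 0.25 mL of 1% buffered lidocaine delivered by the J-tip injector". For the comparator: "Group 2 will be formed by subjects receiving 1.5 mL of 1% plain lidocaine injected by syringe and 25 gauge needle".
- **Injection procedure.** For the J-Tip: "One quarter of a milliliter of one percent lidocaine will be injected". For the comparator: "25 gauge needle injection of 1% lidocaine ninety seconds prior to introduction of the regional block needle". Neither states a formulation.

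Buffering appears in only one other place, the title of a cited study in Section 14, which says nothing about the drug used here.

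Section 4 also lists what is to be recorded. The list of times opens with "Times will be recorded for; time of J-tip administration, time of regional block performance, operating room arrival time". Of drugs, it says that pain and anti-nausea "medication use will be recorded in PACU and by the patient on the first three post-operative days". The formulation of the local anesthetic is not among the listed items.

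Infiltration pain is a secondary objective (Sections 1.7 and 3.2). On how it is scored, Section 4 says: "The scale immediately after will be with regard to pain felt at time of J-tip use or needle introduction". The Results text accompanying Tables 3 and 8 interprets the injection-type coefficient as a fall of about 2 VAS points caused by giving a J-Tip injection.

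**The concern.** One of the two definitions of the experimental drug must be wrong, and nothing in the documents says which. A reader cannot tell what the 57 J-Tip patients in Table 1 received and could not reproduce the treatment.

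The conflict also falls on the outcome that carries the positive finding. In the Results supplied, the infiltration scores are the only outcomes reported as different between arms, and they are taken as the solution is delivered. If only the J-Tip arm had buffered lidocaine, a second drug-related difference would travel with the device, beside the difference in volume. The Results sentences speak of the J-Tip injection as the cause and mention neither difference. What is at stake is how the two-point difference is attributed, not whether it exists.

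**Working it through.** **1. Formulation statements in Section 4, side by side**

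| Place | J-Tip arm | Needle arm |
|---|---|---|
| Opening paragraph | 0.25 mL, 1% plain | 1.5 mL, 1% plain |
| Group definitions | 0.25 mL, 1% buffered | 1.5 mL, 1% plain |
| Injection procedure | 0.25 mL, 1%, not stated | 1%, not stated |

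The needle arm is consistent. The J-Tip arm is plain once, buffered once and unspecified once.

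**2. Reproduce the reported differences (inputs from Table 1)**

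Femoral: needle 3.57 (SD 2.133, n = 54), J-Tip 1.54 (SD 1.524, n = 57). Table 2 gives p = .036 for equality of variances, so I use the unequal-variance form.

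- Difference = 3.57 − 1.54 = 2.03.
- SE = √(2.133²/54 + 1.524²/57) = 0.354, with 95.5 df.
- 95% CI 1.328 to 2.732, as in Table 2.

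Sciatic: needle 4.500 (SD 2.4553, n = 54), J-Tip 2.272 (SD 2.1631, n = 57). The variance test gives p = .474, so I use the pooled form.

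- Difference = 4.500 − 2.272 = 2.228.
- Pooled variance = (53 × 2.4553² + 56 × 2.1631²)/109.
- SE = √[pooled variance × (1/54 + 1/57)] = 0.4386, with 109 df.
- 95% CI 1.359 to 3.097, as in Table 2.

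Adjusted coefficients for J-Tip (Tables 7 and 11), with t(0.975, 100 df) = 1.984:

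- Femoral: −2.020 ± 1.984 × 0.322 = −2.659 to −1.381 (Table 7: −2.660 to −1.381).
- Sciatic: −2.248 ± 1.984 × 0.433 = −3.107 to −1.389, as in Table 11.

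The reported differences are therefore sound as arithmetic.

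**3. What the contrast can identify**

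Let A = 1 for J-Tip and 0 for needle. Let V be the volume in mL, and F = 1 for buffered and 0 for plain.

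- In both versions V = 1.5 − 1.25A. The ratio is 1.5/0.25 = 6. At 1% (10 mg/mL) the doses are 2.5 mg and 15 mg.
- If the group definition was followed, F = A as well.
- If the opening paragraph was followed, F = 0 for everyone.

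V is an exact linear function of A in both cases, and F equals A in the first. No regression can separate terms that move together perfectly. The models behind Tables 7 and 11 adjust for gender, age, ethnicity, BMI and thigh circumference, which does not touch this. The coefficient on injection type is device plus volume under the plain version, and device plus volume plus formulation under the buffered version. It is never device alone.

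**4. Range, by assumption only**

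The documents give neither size nor sign for the part due to formulation or volume. Call that part b, in VAS points. The device remainder is the difference minus b, with both confidence limits shifted by b.

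| Assumed b | Femoral remainder (95% CI) | Sciatic remainder (95% CI) |
|---|---|---|
| −0.5 | 2.53 (1.83 to 3.23) | 2.73 (1.86 to 3.60) |
| 0 | 2.03 (1.33 to 2.73) | 2.23 (1.36 to 3.10) |
| 0.5 | 1.53 (0.83 to 2.23) | 1.73 (0.86 to 2.60) |
| 1.0 | 1.03 (0.33 to 1.73) | 1.23 (0.36 to 2.10) |
| 1.5 | 0.53 (−0.17 to 1.23) | 0.73 (−0.14 to 1.60) |

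The lower limit for a device-only effect reaches zero when b is about 1.33 (femoral) or 1.36 (sciatic). This shows how much would be needed. It is not evidence that b is of that order.

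**5. Exposure of the primary outcome**

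Section 4 places block pain mainly at the muscle fascia, which it says no local anesthetic reaches. The Results report no significant difference in VAS immediately after the femoral or sciatic block. There is no positive primary finding whose attribution depends on formulation.

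**The case against.** The strongest reply is that this is one conflicting word in a trial that compares two ways of giving local anesthetic as they are delivered. The objectives set J-Tip injection against needle injection and never claim to isolate the device from drug or volume. On that reading the randomized contrast answers the question asked, whatever was in the cartridge. No passage says that buffering alters injection pain. In the needle arm the score is tied to needle introduction, so pain from the solution may be only partly captured.

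Most of this stands. The technique comparison is valid, no estimate changes, and the clinical weight of buffering cannot be drawn from these documents. What does not fall away is that the experimental treatment has two definitions, and the buffered one sits where the randomized groups are defined, so it cannot be dismissed as the slip.

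A reader might infer that everything turns on the formulation, so that proof of plain lidocaine in both arms would let the result sentences stand as a statement about the device. The documents do not support that, because the six-fold volume difference is in both versions. A reader might also infer that the formulation can no longer be found out. The recording list in Section 4 omits it, but that does not show that anesthesia or pharmacy records lack it.

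**Conclusion.** The contradiction is certain and is resolved nowhere in the documents. Its consequence is limited. Formulation is a possible further difference between arms, fully aliased with the device if the group definition was followed. Volume is a definite one in either case. The infiltration differences of 2.03 (1.33 to 2.73) and 2.23 (1.36 to 3.10) VAS points stand as differences between techniques and cannot be assigned to the device alone.

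It would go too far to say that buffered lidocaine was given, that buffering explains part of the two points, or that the comparison is invalid. The documents give no direction or size for such an effect and do not show which drug was used. Sample size, the reported estimates and the primary outcome are unaffected. I grade this minor to moderate: an internal inconsistency in the definition of the intervention that bears on the wording of the main positive result.

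**What to change.** **As a plan.** Use one formulation in both arms: 1% plain, as the opening paragraph of Section 4 already has it. Say so in the group definition and for both arms in the injection procedure. This removes an avoidable difference between arms. It does not isolate the device, because the volumes still differ.

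**For the 57 J-Tip and 54 needle patients already treated.** First establish the formulation from existing anesthesia or pharmacy records. Only then make the three descriptions in Section 4 agree with what was given, or state that it could not be established. Changing the group definition to plain before checking could make the document misreport the treatment.

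**Whatever the records show.** Reword the two sentences that interpret the injection-type coefficient (text with Tables 3 and 8), for example:

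> VAS was about 2 points lower with the J-Tip technique (0.25 mL) than with the needle technique (1.5 mL). The techniques differed in device and volume, and [differed / did not differ / may have differed] in lidocaine formulation, so the difference is not attributed to the device alone.

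**Cost.** A records check, which may not give an answer; edits to Section 4 and two result sentences; and a slightly narrower conclusion. No new data and no re-analysis are needed.

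### The plan does not withhold the arm from the surgeon or PACU staff, whose decisions shape secondary outcomes, or say that the anesthesiologist's telephone pain scores stay out of the comparison

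*Combined protocol and SAP*

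**What the plan says.** Section 1.3 gives the design in one sentence, "This study is a prospective and randomized project", and neither it nor any other section provides masking. The word double-blind occurs only in the title of a cited study.

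On who knows the arm, section 4 says "A single anesthesiologist will perform all J-tip or needle local anesthesia injections and nerve blocks in this study". The child is not yet under general anesthesia at that point, and the lidocaine is "injected with the characteristic “pop” and “hissing” sounds inherent to the J-tip injector".

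On post-operative pain, section 4 has two parallel sources. One is the child: "The patient will record visual analogue pain scales on post-operative days one through three". The other is a call: "The anesthesiologist will collect telephone verbal pain scores on a 0-10 scale on post-operative days one and two". The call is described as usual care for everyone who has a block. Section 3.2 names the VAS as the instrument for post-operative block efficacy. Section 1.7 speaks only of pain levels up to day three, and section 7 names no outcome at all.

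On staff-dependent outcomes, section 3.2 lists pain medication and anti-emetics given in PACU, and PACU stay in minutes: "To evaluate time in PACU with use of J-tip compared to needle use group prior to regional block". On co-treatment, section 4 says only "It will also be recorded if intra-articular analgesic injection is given intra-operatively".

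**The concern.** Outcomes that depend on a staff decision can differ between arms simply because staff know the arm. A nurse may give an analgesic sooner or later, a discharge may be brought forward or held, or a surgeon may be more inclined to inject the joint in one arm. A caller who knows the arm may also ask about or record pain differently. Either route can produce a difference where none exists or cover a real one, and recording the co-treatment does not remove the effect.

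At stake is the secondary question of whether the J-Tip changes post-operative block efficacy, medication use and recovery time, which section 10.2 lists as a possible benefit. The protocol takes care over other influences on the pain scores: parents leave the room, screens and music are off, and earlier scores are hidden from the child. It takes no comparable step against staff knowledge of the arm after the block.

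**Working it through.** **Step 1. Which outcomes could be shielded.** Setting sections 3.2 and 4 side by side:

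| Measure | Who decides or records | Can the arm be withheld from that person? |
|---|---|---|
| Pain from the local injection and from the block | Child, before surgery | No; staff conduct after the block cannot affect it |
| PACU analgesic and anti-emetic amounts | PACU staff | In part |
| PACU minutes | PACU staff | In part |
| Intra-articular analgesic (co-treatment) | Surgical team | In part |
| PACU VAS | Child | No |
| Telephone score, days 1-2 | Child's answer, taken by the anesthesiologist | Not from the child; not from the caller if the caller gave the injection |
| Home VAS and medication logs | Child, at home | No |
| Satisfaction | Child and parent; "The questionnaire will be specific to the patient's randomized treatment group" | No |

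The answer is in part for staff because the child may mention the device, and because a complete drug record shows 0.25 mL in one arm and 1.5 mL in the other.

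**Step 2. Is the caller the injector?** Section 4 introduces a single anesthesiologist for all injections and later writes of the anesthesiologist who telephones. Identity is the natural reading, but it is inferred. The text does not name the caller's role further.

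**Step 3. Size.** The only planning figures are 50 per group and 115 enrolled, and 2 x 50 + 15 = 115 reproduces. No alpha, power, effect or SD is given, and nothing is given for PACU drug amounts, PACU minutes or intra-articular use, so no bias in those can be computed.

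For a 0-10 pain score an illustration is possible. Assume a two-sided 5% test, 50 per arm and SD 1.5 to 2.5. (Table 1 of the Results shows SDs of 1.524 to 2.4553, but for pain just after the local injection.)

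- SE = SD x sqrt(2/50) = 0.2 x SD = 0.30 to 0.50 points.
- Detectable difference at 80% power = (1.960 + 0.842) x 0.2 x SD = 0.56 SD = 0.84 to 1.40 points.
- With no true effect and a systematic bias b, the false-positive rate = Phi(-1.96 + b/SE) + Phi(-1.96 - b/SE):

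| b (points) | SD 1.5 | SD 2.0 | SD 2.5 |
|---|---|---|---|
| 0.25 | 13.3% | 9.6% | 7.9% |
| 0.50 | 38.5% | 24.0% | 17.0% |

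For co-treatment, shift = difference in use x effect. If use differed by 10 to 20 percentage points and the injection lowered PACU VAS by 1 to 2 points, the shift would be 0.10 x 1 = 0.1 to 0.20 x 2 = 0.4 points. Both inputs are assumptions, and PACU VAS is not one of the staff-decided outcomes.

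**Step 4. What is already reported.** The Results list VAS before PACU discharge among the comparisons without a significant difference. They show no PACU drug amounts, PACU minutes, telephone scores or intra-articular use by arm, so a reader cannot see whether co-treatment was balanced.

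**The case against.** A reader might infer that an unblinded operator scores a stated efficacy outcome. The documents do not support this. Section 3.2 names the VAS, the child records it at home, and the call is usual care. What stands is narrower: no sentence excludes the telephone score from the comparison, and section 1.7's wording leaves room for it.

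A reader might also infer that everyone after the block could be blinded, or that staff are told the arm. Neither follows. The child hears the device and can speak of it, and home logs, home VAS and satisfaction stay unmasked whatever staff know. The plan is silent on disclosure to staff; the finding is that nothing prevents it.

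Nor do the documents show that the surgeon and PACU nurses have no need of the arm. The arms differ in lidocaine volume, and treating staff may want that information. This objection stands against removing the drug from the chart, but not against leaving the arm out of the verbal handover.

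On size, the illustrative shift of at most 0.4 points lies below the 0.84 to 1.40 points detectable at 80% power. That is fair, but a bias need not be detectable to matter: 0.25 points already raises a 5% error rate to about 8-13% under the same assumptions.

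One surgeon does all the operations, which removes variation between surgeons. It does not stop one surgeon who knows the arm from treating the arms differently. Section 7 permits regression adjustment, but intra-articular use is decided after randomization, so adjusting for it would not reliably undo the effect.

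**Conclusion.** The point holds for secondary post-operative outcomes only. As written, the plan leaves an avoidable source of bias in PACU analgesic and anti-emetic amounts, PACU minutes and the use of intra-articular analgesic. It also leaves open whether a telephone score, probably taken by the unblinded operator, enters the comparison.

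The conclusion rests on the absence of any masking provision and on the natural reading that the caller is the injecting anesthesiologist. The size and direction of any bias are unknown. The percentages above are illustrations under an assumed SD, alpha and bias, and apply to a 0-10 pain score, not to PACU drugs or minutes. Pain from the block and pain from the local injection are scored before surgery, so the primary objective is not in doubt on this ground. This is a low-cost improvement, not a threat to the main comparison.

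**What to change.** In section 4, where randomization and post-operative scoring are described:

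1. State that the surgeon and PACU staff are not told the arm at handover until PACU discharge. Keep the allocation on the study sheet, leave the medical record of drugs given complete, and make the arm available at once if needed for safety.
2. State that the child's self-recorded VAS, the instrument in section 3.2, is the only day 1-3 pain measure compared between arms, and that the telephone scores are routine follow-up.
3. Report intra-articular analgesic use by arm as n/N, and state that home-recorded outcomes and satisfaction are unmasked.

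For patients already treated, only items 2 and 3 can be applied, with a statement that post-operative outcomes were unmasked.

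The cost is a few protocol sentences and a handover instruction, with no added staff or procedures. The downsides are that masking stays incomplete, since the child may reveal the arm and the drug record shows it, and that the telephone scores no longer serve as an efficacy measure.
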